- **Decliners:** We will thank them for their time, not gather any information, and not contact them again.
- **Accepters:** The recruiter will briefly describe the study and give the couple a

study brochure (NEXUS Recruitment Brochure for the Well-child cohort: Appendix 10) that describes study procedures, genomic sequencing, the kinds of conditions that could be identified, the randomization process, and a decision aid to help them make a decision about joining the study. They will also be given a copy of the consent form (NEXUS Recruitment Brochure for the Well-child cohort: Appendix 10) about joining the study to read and the intake form for each member of the couple (or just for mothers if they are participating without a partner). The intake form collects information about demographics, previous experience with genetic testing, knowledge about genomic sequencing, and pregnancy anxiety. Couples will be asked to complete this form and bring it with them to the study visit.

The couple will be asked if they will agree to being contacted by phone by the study scheduler to ascertain their interest in joining the study. Couples who agree will be asked for their phone number and contact information, including email address, and their language preference, which will be entered into the study database (REDCap) along with the clinic from which they were recruited and gestational age of the pregnancy. The recruiter will provide a timeframe for the call (e.g., a week) and ask that both members of the couple read the study brochure and informed consent form before that time and be present on the call.

For those who agree to join, the recruiter will offer access to the first questionnaire (T1Q) in either paper form or electronic links. iPADS will be available for use by those who do not have a smart phone or other device. If both members of the couple are present and have time, they can also access the first decision guide. Alternatively, if participants wish to wait until they leave the clinic, or for times when the partner is not present, study staff will email the links to the T1Q (see below).

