Participants will also be sent links to the first electronic decision guide; these links become active after the completion of the T1Q. For couples, each parent will complete the questionnaire independently. The link will take them to a copy of the information page that will instruct them that by proceeding to the questionnaire, they will have agreed to join Phase I of the study.

Recruitment phone call: The study scheduler will call the couple and ask if they would like to join the study.

- **Decliners:** Couples who indicate they are not interested in joining the study will be asked to provide basic demographic data and a reason for declining. Completion of this step will end their participation and their identifying information will be shredded.
- **Accepters:** We will obtain the **couple's verbal consent** for Phase 1; joining the study.

If both parents have not read the study brochure and the consent form by the time the scheduler calls, they will be given additional time to read it, agreeing on how much time that will be.

Parents who have access to an Internet-enabled computer will then be provided with a link to access the Time 1 questionnaire. Each member of the couple will complete the questionnaires in the study independently.

After completing the Time 1 questionnaire, they will be given access to the online electronic decision aid. The decision aid will provide information about sequencing and the types of results available, the frequency of such findings, the risks and benefits of study participation, and guide parents thru the decision-making process. Parents will be encouraged to view the decision aid before the study visit and can use it to indicate their choice of one of three options:

- (1) not interested and do not wish to schedule a visit, or
- (2) interested and want to schedule a study visit, or
- (3) undecided and want to schedule a study visit to learn more.

Thus, couples are **not** expected to make a decision at this time and will have ample time to gather information and consider their options.

Parents who do not have internet access will be mailed a copy of the Time 1 questionnaire with instructions to return the completed copy in a pre-paid envelope. They will then view the decision aid at the study visit.

Those who agree to a study visit will be scheduled and sent information about the appointment time, date and location of the visit.

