- **Non-compliant decliners:** Couples who verbally consent to the study but who do not successfully schedule a study visit or who fail to appear for their scheduled study visit will be asked if they would be willing to reschedule their visit. If not, they will be considered to be decliners. Decliners will be asked to provide basic demographic information (for comparison to the accepters) and their reasons for declining. Completion of this step will end their participation in the study.

Study Visit Activities: Couples who schedule a study visit will meet in person with a genetic counselor who will collect their completed intake form, assess their health literacy and numeracy with a validated brief interview, and discuss any issues generated by the electronic decision aid about accepting or declining sequencing of their child. The counselor will answer questions and assess their understanding of main points of informed consent including the range of results that could be returned, the planned use and storage of genetic data as well as the risks and benefits of genomic sequencing.

Consent (for Phase II; sequencing) will be obtained from both members of the couple except in cases where the father is not reasonably available. In those cases only the mother will be consented.

In cases when one parent is unable to attend the study visit, we will use Skype for the counseling and consent process. The Skype counseling and consent will be done in the CTRC and will be conducted by the clinical geneticist and/or genetic counselor. The partner who is unable to attend will sign the consent form during the encounter and return it to the study office.

- **Sequencing consenters:** After consenting, couples will complete the Time 2 questionnaire about their decision, mood, and knowledge about the project. They will also be asked to provide consent for access to their child's state newborn screening results and pertinent medical records.
- **Sequencing decliners:** Parents who decline sequencing will be asked to complete the Time 2 questionnaire and will exit the study.

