- A. Clinical actionability curation: Curated literature review data for each gene-disease pair will be stored in a REDCap database. Final scores determined by the binning committee will be recorded and analyzed.
- B. Definition of categories of genomic information: Based on curation of age of onset and actionability, the binning committee will determine thresholds that define the four categories of genomic information as described in section 2.
- C. Observational study of outcomes and integration of findings into clinical

care: Longitudinal outcomes data will be collected in a REDCap database and analyzed.

Primary Objective 3:

Consistent with the primary research questions for this objective, which focus on ethical use of NGS-NBS, we specify the following primary independent variables: Race/ethnicity (non-Hispanic White, Black, Hispanic), health literacy, and child status (diagnosed vs. well). We specify the following primary dependent variables: sequencing-related distress, knowledge about NGS-NBS and (for the “decision group” only) about additional genomic results (continuous variables), decision to accept or decline NGS-NBS and (for the “decision group” only) additional genomic results (dichotomous variables), and decisional conflict (a continuous variable). Primary analyses will focus on these outcomes in mothers. These analyses involve a between-within design and will be analyzed with mixed linear modeling to accommodate nesting (i.e., assessments nested within participants). Models with continuous outcomes will be implemented with SAS PROC MIXED because (a) it can handle nested data; (b) it handles missing data more appropriately than repeated-measures analysis of variance, which uses listwise deletion of missing data; and (c) it provides a wider range of options for modeling the error covariance structure than general linear model procedures, which assume an error structure that is often unrealistic. Models with dichotomous outcomes will be implemented using mixed-effects logistic regression within SAS PROC GENMOD, which shares strengths similar to those offered by PROC MIXED.

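### Health literacy is described as measured only at the in-person visit, so parents who decline NGS-NBS before it have no described score and would fall out of a literacy model of that decision

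*Combined protocol and SAP*

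**What the plan says.** Under Outcome data and data analysis, Primary Objective 3, health literacy is one of three primary independent variables, beside race/ethnicity and child status. The primary dependent variables include the "decision to accept or decline NGS-NBS", and the primary analyses are in mothers.

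The literacy measurement is described once, under Recruitment and enrollment procedures, Study Visit Activities: "Couples who schedule a study visit will meet in person with a genetic counselor who will collect their completed intake form" and will "assess their health literacy and numeracy with a validated brief interview". The Diagnosed Cohort text refers back to the same visit.

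The same section provides two ways to decline before that visit. One of the three choices after the decision aid is "not interested and do not wish to schedule a visit". Couples who gave verbal consent but do not schedule or attend are asked to reschedule: "If not, they will be considered to be decliners". For this second group the data are limited: "Decliners will be asked to provide basic demographic information (for comparison to the accepters) and their reasons for declining".

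The intake form is handed in at the visit and lists no literacy item: "The intake form collects information about demographics, previous experience with genetic testing, knowledge about genomic sequencing, and pregnancy anxiety". The Study design narrative also offers the Time 1 questionnaire to parents who decide against a visit, but does not itemise it. The full list of measures is in Appendix 19, which is not among the documents. The only remark on missing data contrasts PROC MIXED with repeated-measures analysis of variance; nothing is said about a missing predictor.

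**The concern.** Formal consent to sequencing is taken at the visit, so accepters pass through the literacy interview. Among enrolled parents, only decliners can miss it by design. A primary predictor would then be absent on one side only of a primary outcome.

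Two things are at stake. The first is precision: decliners are the smaller outcome group, and the information about a log odds ratio depends mostly on the smaller group. The second is bias, if the decliners who leave before the visit differ in literacy from those who decline at it. That is plausible, because the early exit follows an aid that parents normally work through at home, before any counselor has helped them. It cannot be checked without scores for those who left, and a score not collected before a parent exits cannot be recovered later.

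**Working it through.** **1. The plan's own figure.** Sample size determination states 83% power for a 12-point difference in acceptance between cohorts (70% in the well-child group, odds ratio 2.0, p-value 0.05). An odds ratio of 2.0 from 70% gives 82.35%. With 200 per cohort, two-sided, z = (0.1235 × √200 − 1.96 × √(2 × 0.7618 × 0.2382)) / √(0.70 × 0.30 + 0.8235 × 0.1765) = (1.747 − 1.181) / 0.596 = 0.95, so power is 82.9%. The figure reproduces, but it compares cohorts. No power is stated for literacy as a predictor of the decision.

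**2. Who has a described score.**

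| Route | Outcome | Literacy score described? |
|---|---|---|
| Attends visit, consents | accept | yes |
| Attends visit, declines | decline | yes |
| Not interested after decision aid | decline | no |
| Never schedules or attends | decline | no |

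**3. How many decliners.** From Anticipated Number of Research Subjects, 250 + 350 = 600 family units are enrolled to sequence 200 + 200 = 400.
- Upper bound: 600 − 400 = 200.
- At the plan's acceptance rates (80% diagnosed, 70% well-child): 250 × 0.20 + 350 × 0.30 = 50 + 105 = 155, leaving 445 accepters.

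The share of decliners who leave before the visit is not given. One half and three quarters are used below as assumptions.

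**4. Precision.** For a given spread of literacy, information about its log odds ratio is roughly proportional to N·p·(1 − p) = accepters × decliners / N. The SE ratio is the square root of the ratio of informations.

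| | All scored | Half lost | Three quarters lost |
|---|---|---|---|
| 200 decliners: N; acceptance | 600; 66.7% | 500; 80.0% | 450; 88.9% |
| Information | 400×200/600 = 133.3 | 400×100/500 = 80.0 | 400×50/450 = 44.4 |
| SE ratio | 1 | √(133.3/80.0) = 1.29 | √(133.3/44.4) = 1.73 |
| 155 decliners: N; acceptance | 600; 74.2% | 522.5; 85.2% | 483.75; 92.0% |
| Information | 445×155/600 = 115.0 | 445×77.5/522.5 = 66.0 | 445×38.75/483.75 = 35.6 |
| SE ratio | 1 | √(115.0/66.0) = 1.32 | √(115.0/35.6) = 1.80 |

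**5. Power, for illustration.** With 200 decliners, literacy split 50/50, odds ratio 2.0 and loss unrelated to literacy, two-sided power is 0.978 with all scored, 0.861 with half lost and 0.614 with three quarters lost.

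**6. Bias.** Let a and b be the shares of low- and high-literacy decliners who leave before the visit. Accepters are unaffected, so

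observed OR = true OR × (1 − a) / (1 − b).

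- a = b = 0.50: 2.0 × 0.50/0.50 = 2.0, no bias.
- a = 0.75, b = 0.50: 2.0 × 0.25/0.50 = 1.0, the effect disappears.
- a = 0.75, b = 0.25: 2.0 × 0.25/0.75 = 0.67, the effect reverses.

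**The case against.** The strongest reply is that measurement only at the visit cannot be proved from these documents. Time 1 is meant to show how interested and uninterested parents differ, its items are not listed, and Appendix 19 is not available. The protocol body is not a full inventory of measures: trust in the medical community is a planned control variable, yet no section says when it is collected. This stands, and the point is therefore conditional on what Time 1 contains.

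Other replies also stand in part:
- The 200 families not sequenced include dropout, ineligible newborns, inadequate samples and parents who withdraw consent after the visit and already have scores. It is an upper bound.
- Some routes keep decliners in: undecided parents may book a visit, and parents without internet access see the decision aid there. With half lost, the illustrative power of 86% still exceeds the plan's 83% benchmark.
- The study describes itself as exploratory, and this is one predictor-outcome pair among several.

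A reader might infer more than the documents support. Missingness that follows the outcome does not by itself bias the literacy odds ratio; step 6 shows that equal loss leaves it unchanged. Nor does it follow that race/ethnicity or cohort comparisons of acceptance lose these parents: the plan does not say which predictors enter that model together, and those comparisons need no literacy score. No complete-case rule is stated either. Omission is an inference: a regression cannot use a record without its predictor unless imputation or a similar method is added, and none is planned.

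**Conclusion.** The point holds on the protocol body, provided that neither Time 1 nor Appendix 19 already contains a literacy measure. A model of accept/decline on literacy would then keep the accepters and the decliners seen at the visit, and omit those who declined earlier.

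The loss of precision is about 1.3 times the standard error if half the decliners leave early, and 1.7 to 1.8 times if three quarters do. Those shares are assumptions, applied to 155 decliners or to the upper bound of 200. Bias is possible but not shown: it requires that, among decliners, leaving before rather than at the visit depends on literacy. The fall from 2.0 to 1.0 illustrates how sensitive the estimate is and is not a forecast.

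This should be fixed because the remedy is cheap and the missing scores cannot be recovered. A reader might go further and call the Objective 3 analysis invalid. The documents do not support that: most predictor-outcome pairs are not shown to be affected, and the size of the loss is unknown.

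**What to change.** 1. Confirm whether Time 1 or Appendix 19 contains a literacy measure. If so, name it in the analysis section as the source of the primary predictor; no further change to data collection is needed.
2. If not, give all Phase I parents a brief validated literacy measure, suited to self-completion or telephone, with Time 1 and before the decision aid opens. The visit interview is not named, so whether it can be given this way needs checking. The recruitment procedures place Time 1 before the decision aid, but the Study design narrative places it after the decision about a visit; reconcile these so that the score precedes the decision.
3. Fit the accept/decline model on all Phase I mothers.
4. For mothers already enrolled without a score, multiply impute from the demographics and Time 1 data actually held, with the decision in the imputation model, and show the complete-case analysis as a sensitivity analysis. Imputation assumes that early decliners resemble visit decliners given those data, so it is second best to measuring.

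Cost: a few minutes of added burden before the first decision, and a small amendment. The Study design narrative already allows measures to be added, on user-testing feedback, with a 5-day notice to the FDA.

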An aliquot from each uniquely coded DNA sample will be transferred by the BSP to the lab of [name], MD, PhD, Associate Professor in the Department of Genetics at UNC. Samples will be subjected to NGS using whole exome sequencing (WES) as described in section 2. (Agilent SSEL Automated Target Enrichments: see Appendix 5). Sequencing libraries will be transferred to the HTSF for massively parallel sequencing using the Illumina HiSeq 2000 or HiSeq 2500 platform (Appendix 6).

Changes in technology may alter the choice of target capture or sequencing platform, which might affect the yield of positive results but would not affect the nature of results returned.

Bioinformatics:

Raw sequence data from the HTSF will be analyzed using standard bioinformatics methods to map sequence fragments and align them to the reference human genome. Genetic variants will be identified using a custom pipeline that has been developed in collaboration with colleagues in the Department of Genetics and the Renaissance Computing Institute (RENCI). The current pipeline is as follows:

- Fragments are aligned against an indexed reference human genome (NCBI 37.1 / hg19) using BWA
- Resulting SAM files are sorted, indexed, and converted to binary BAM files using Picard and SAMtools.
- Post-alignment optimization, including PCR duplicate removal, realignment of reads, and quality score recalibration are performed using The Genome Analysis Toolkit (GATK).
- Single nucleotide variants and small insertions and deletions are called using the GATK Unified Genotyper.
- Quality metrics will be incorporated so that coverage with quality scores can be assessed for any given nucleotide.

Genetic variants identified (approximately 100,000 per individual exome) will be deposited in a dedicated database and will be extensively annotated and subjected to *in silico* analysis. Annotations that will be applied to the variants and reviewed by the analysts who interpret the variants are as follows:

- RefSeq transcripts, with protein effects
- 1000 genomes project and Exome Aggregation Consortium (ExAC) variant frequency data
- Human Gene Mutation Database (HGMD) mutations and ClinVar pathogenicity assertions
- Additional annotations are possible, such as dbSNP entry, OMIM identifiers, evolutionary conservation, Polyphen and other protein prediction algorithms.
- Curated references from the biomedical literature.

Categorization of possible genomic information:

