In the “Diagnosed Cohort,” we will perform an “indication-based analysis” that evaluates variants in genes within a specific diagnostic list that is constructed so as to interrogate all known genes that could be related to a patient’s phenotype. In the setting of a diagnostic evaluation, we will review all variants in genes that could be related to the phenotype, using a computational classifier to prioritize variants for analysis (Table 1). Since these individuals are already diagnosed with a rare genetic disorder, we will return variants that are deemed to be “pathogenic,” “likely pathogenic,” or “variant of uncertain significance,” according to accepted practice guidelines developed by the ACMG. It should be noted that the computational prioritization is strictly intended as a way to facilitate human review of the data, and will not constitute an automated assessment of variant pathogenicity. For instance, it has been our experience in prior exome-sequencing related studies that many variants that had previously been identified as pathogenic in databases of human mutation have subsequent evidence calling this pathogenicity into question, supporting the need for manual review of variants even in this high-priority class.

Table 1: Computational classification of genomic variants to prioritize for human review

Class	Present in database of human mutations ¹	Variant Type ²	Minor Allele Frequency (MAF) ⁶
A	Yes	Any	<5%
B	N/A	Truncating ³	<1%
C	N/A	Missense	<1%

D	N/A	Synonymous, Non-canonical splice site ⁴ , and UTR ⁵	<1%
E	N/A	Intronic	<1%
F	N/A	Truncating and Missense	1-5%

G	N/A	All other variants	1-5%
H	N/A	Any	>5%

1. Databases to be used in this computational analysis include HGMD and the NCBI ClinVar database. Variants that qualify for category A are those identified as “Disease Mutation” (DM) in the HGMD or variants identified as “Pathogenic” or “Likely Pathogenic” in ClinVar.

2. For the purpose of computational classification, the “variant type” will default to the most damaging effect for the variant among all of the transcripts represented in the RefSeq database. For example, if the variant has a missense effect in one transcript but is intronic or UTR in another transcript, it will be treated as missense for the purposes of computational classification.

3. Truncating variants include: nonsense, frameshifting insertions/deletions, and canonical splice site alterations (the first two and last two nucleotides of the intron).

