4. Non-canonical splice site variants include those that occur within 3-10 nucleotides of the intron-exon border.

5. UTR variants are annotated as being located in the 5’ untranslated or 3’ untranslated regions of the mRNA.

6. MAF data will be derived from frequency data from the 1000 Genomes Project and ExAC; the highest of the minor allele frequencies for a given variant from any ethnic group will be used to evaluate the MAF threshold criteria.

Integral to the efficient diagnostic assessment of an entire genome or exome will be the establishment of *a priori* panels of genes to be assessed under certain clinical situations. One of the major tasks of the clinical and molecular teams will be the development of such lists relevant to the categories of disorders that are present in the Diagnosed Cohort. Once established, these lists will be used to query patients’ variant data to identify all variants in genes of possible diagnostic significance in the context of their medical presentation. A molecular analyst will evaluate the prioritized variant list and provide a preliminary interpretation of the case to the molecular sign-out committee.

The committee will make a final pathogenicity determination and decide whether any variants exceed our threshold for reporting (Table 2). Because of the presence of a phenotype in the individual being sequenced, results considered to be clinically relevant would include the “known pathogenic,” “likely pathogenic,” and “variant of uncertain significance” as determined by the molecular sign-out committee.

Table 2: Categories of findings deemed reportable for an indication-based analysis

Result Category	Variant types	Zygosity	Phenotype ⁸	Inheritance
Positive-Definitive	KP ¹	Heterozygous	Concordant	Dominant ⁹
	KP	Homozygous or compound heterozygous ⁶	Concordant	Recessive ¹⁰
Positive-Probable	LP ²	Heterozygous	Concordant	Dominant
	KP	Potentially compound heterozygous ⁷	Concordant	Recessive

	LP	Homozygous or potentially compound heterozygous	Concordant	Recessive
--	----	---	------------	-----------

Uncertain-VUS	VUS ³	Heterozygous	Concordant	Dominant
	VUS,	Homozygous	Concordant	Recessive
	VUS plus KP/LP ⁴	Compound heterozygous or potentially compound heterozygous		
Uncertain-AR het	KP/LP ⁵	Heterozygous	Concordant	Recessive
Uncertain-Contributory	Any	Any	Partially matching	Any

1. KP = Known Pathogenic

2. LP = Likely Pathogenic

3. VUS = Variant of Uncertain Clinical Significance

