In the “Well-Child” cohort there will be no phenotype to inform a diagnostic list. In addition, all conditions unrelated to the phenotype known for patients in the “Diagnosed Cohort” would be considered “incidental” to their primary indication for sequencing. Therefore, the analysis of the NGS-NBS list and additional genomic findings will be more akin to screening than diagnostic testing. In this setting, the prior probability that an individual has a rare Mendelian disorder will be very small (based on the population prevalence of the disorder), and thus the positive predictive value of genomic information will be strongly influenced by the specificity of the results. Both the “Diagnosed Cohort”

and “Well-Child Cohort” will receive results from the “NGS-NBS” gene list. In order to minimize false positives, we will use stringent criteria for return of results and will only return variants that are deemed to be “pathogenic” or “likely pathogenic” and consistent with the expected inheritance pattern of the condition (eg. homozygous or presumed compound heterozygous variants in the case of a recessive condition).

Variants will be computationally selected for their presence in a gene on the NGS-NBS list, their likely pathogenic significance and, in the case of recessive conditions, whether one or two mutations are present (34). Given the large number of possible genomic findings, and the low *a priori* likelihood that individuals in the “Well-Child” cohort would be affected with any given rare genetic disorder, it will be critical to strike a balance between the “sensitivity” and the “specificity” of the analysis so as to correctly identify individuals at high risk for a treatable genetic condition without overwhelming the molecular analysts, MGL, and clinicians with large numbers of variants of uncertain significance. This analysis will utilize the same computational classes as described in Table 1, with additional informatic filtering to determine which variants qualify for human review. We will review variants that satisfy the following conditions:

- 1) For genes associated with conditions inherited in a dominant fashion, we will review any variants in computational classes A and B;
- 2) For genes associated with conditions inherited in a recessive fashion, we will review variants in cases where two or more variants from computational classes A, B, or C are present.

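### Table 1 has no class for rare, unlisted in-frame insertions or deletions, so the recessive screening filter cannot count them and can report an affected child as negative without review

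*Combined protocol and SAP*

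**What the plan says.** The Bioinformatics section states that "Single nucleotide variants and small insertions and deletions are called using the GATK Unified Genotyper", so in-frame insertions and deletions reach the classifier.

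Table 1 (Indication-based analysis) assigns classes by database status, variant type and minor allele frequency (MAF). Four statements matter here:

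- Note 1, on the database route: "Variants that qualify for category A are those identified as" disease mutations in HGMD, or pathogenic or likely pathogenic in ClinVar. Any variant type qualifies if MAF is below 5%.
- Note 2, on variant type: it "will default to the most damaging effect for the variant among all of the transcripts represented in the RefSeq database".
- Note 3, on class B: "Truncating variants include: nonsense, frameshifting insertions/deletions, and canonical splice site alterations".
- The only row for remaining types is class G, "All other variants", at MAF 1-5%.

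The section NGS-NBS and Additional Genomic Findings applies the same classes to screening. For dominant genes, classes A and B are reviewed. For recessive genes, "we will review variants in cases where two or more variants from computational classes A, B, or C are present". Cases that do not meet these rules are reported as negative. Of the reviewed cases, only those with known or likely pathogenic variants that fit the inheritance pattern are returned.

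**The concern.** A classifier that decides what a human looks at should give every called variant a class. Here one type of protein-altering variant falls outside the table only when it is rare and unlisted. The same variant at 1-5% does have a class, so the rarer and more suspicious version is the one left out.

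The recessive rule turns this into a result. A child with one known pathogenic allele and one novel in-frame deletion scores one, not two. The sign-out committee never sees the case, and the parents are told that the screen is negative. Such a miss would come from an incomplete table and would say nothing about exome sequencing as a screening method, which is what the study sets out to learn. It may also surface late or not at all, because false negatives are followed passively, with a chart review at the end of the study.

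**Working it through.** The plan gives no figure on this point, so there is none to reproduce. The check has two parts.

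**1. Is the table exhaustive?** Reading the rows and notes of Table 1 literally, with a MAF from each band (0.1%, 3%, 10%):

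| Variant type | Unlisted, <1% | Unlisted, 1-5% | Listed, <5% | >5% |
|---|---|---|---|---|
| Truncating (note 3) | B | F | A | H |
| Missense | C | F | A | H |
| Synonymous, non-canonical splice, UTR | D | G | A | H |
| Intronic | E | G | A | H |
| In-frame insertion/deletion | **none** | G | A | H |
| Start-loss, stop-loss, if not annotated as another type | **none** | G | A | H |

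All rows A to H are present in the text, so the empty cells are not an extraction fault. In-frame insertions and deletions are the firm case. Note 2 ranks effects across transcripts but does not say how start-loss or stop-loss is labelled.

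Applying the recessive rule (at least two variants in A, B or C):

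- one class A allele and one rare unlisted missense variant: count 2, reviewed;
- one class A allele and one rare unlisted in-frame deletion: count 1, not reviewed, reported negative;
- two rare unlisted in-frame variants: count 0, not reviewed, reported negative.

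**2. How large could the loss be?** Let p be the share of recessive disease alleles that are of this type, below 1% MAF and unlisted. The documents give no value; p = 1%, 3% and 5% are assumptions. With two independent alleles, the share of recessive cases carrying at least one is 1 - (1 - p)^2:

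- p = 1%: 1 - 0.99^2 = 0.0199, or 2.0%
- p = 3%: 1 - 0.97^2 = 0.0591, or 5.9%
- p = 5%: 1 - 0.95^2 = 0.0975, or 9.8%

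These are upper bounds on the false-negative share. A miss also requires that the committee would have judged the variant known or likely pathogenic. An additional A, B or C variant in the same gene would bring the case to review anyway.

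For scale, the Risk Analysis expects findings in fewer than 3% of participants, and the Well-Child Cohort has 200 children: 0.03 × 200 = 6. Treating all 6 as recessive cases, which again overstates the loss:

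- 6 × 0.0199 = 0.12 children
- 6 × 0.0591 = 0.35 children
- 6 × 0.0975 = 0.59 children

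**The case against.** The best defence is that the plan openly accepts imperfect sensitivity in exchange for specificity and a manageable workload. It also treats refinement of the selection algorithm as a core research question, reanalyses earlier participants after an update, and offers an indication-based analysis if symptoms appear. All of this stands and limits the consequences. It does not explain the gap. The recessive rule admits every rare missense variant, so strictness cannot be the reason for leaving out rare in-frame changes. Specificity of what is returned is protected downstream by committee classification and Sanger confirmation.

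Three stronger readings are tempting, but the documents do not support them.

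- *The primary sensitivity outcome is biased.* A reader might infer this because the Diagnosed Cohort uses the same table and "A molecular analyst will evaluate the prioritized variant list". But the Indication-based analysis section says that all variants in phenotype-related genes are reviewed and that the classes serve only to prioritize. Table 2, note 5, also reports a single known or likely pathogenic allele in a recessive gene as uncertain, not negative. An unclassed variant has no stated rank on the list, but it is not excluded.
- *Start-loss and stop-loss are certainly dropped.* An annotator might label them as missense, which is class C. The documents do not say.
- *The percentages are false-negative rates.* They rest on an assumed p and count carriage of such an allele, not missed diagnoses.

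**Conclusion.** The gap is real and follows from the text of Table 1 and note 3 together with the recessive rule. It is firm for unlisted in-frame insertions and deletions below 1% MAF and possible for start-loss and stop-loss. The harm lies in the screening analysis (NGS-NBS and additional findings). The indication-based analysis is not shown to be affected.

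The absolute effect in this study is small: under about 0.6 well children, given p of at most 5%, independent alleles and at most 6 affected children, all with recessive conditions. The true number should be lower, and the documents allow no firmer estimate. The point still merits correction because the omission has no stated rationale, the screening algorithm is itself an object of the research, and the repair is simple.

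**What to change.** - Extend class C to missense and in-frame insertion/deletion, MAF below 1%. The recessive rule then counts these variants without rewording.
- State whether start-loss and stop-loss fall in class B or class C. The choice matters: class B would also bring them into the dominant filter, and class C would not.
- Add a residual class for all other variants below 1% MAF, so that the table is exhaustive, and state which filters, if any, it enters.

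Class F needs no change: it enters neither screening filter, and at 1-5% these variants already fall in G. The dominant rule (A and B) may stay, since it already excludes unlisted missense variants.

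The cost is a few more variants for human review and the 5-day FDA notice. If the change is made after sequencing has started, the Revised results section also requires reanalysis of participants already processed, confirmation of any new finding in the Molecular Genetics Laboratory, and re-contact of parents whose results change. That favours making it early.
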